Appendix 4. Response Assessment Criteria for Chronic Lymphocytic Leukemia (Hallek)⁹

Response	Peripheral Blood ^f	Bone Marrow	Nodes, Liver, and Spleen ^{a,e}
CR	$\begin{array}{c} \text{Lymphocytes} < 4 \text{ x } 10^9 \text{/L} \\ \text{ANC} > 1.5 \text{ x } 10^9 \text{/L}^b \\ \text{Platelets} > 100 \text{ x } 10^9 \text{/L}^b \\ \text{Hemoglobin} > 11.0 \text{ g/dL} \\ \text{(untransfused)}^b \end{array}$	Normocellular < 30% lymphocytes No B-lymphoid nodules ^d	Normal (e.g., no lymph nodes > 1.5 cm)
CRi	Lymphocytes < 4 x 10 ⁹ /L Persistent anemia, thrombocytopenia, or neutropenia related to drug toxicity	Hypocellular < 30% lymphocytes	Normal (e.g., no lymph nodes > 1.5 cm)
PR	$Lymphocytes \geq 50\% \ decrease$ from baseline or $ALC < 4 \times 10^9/L$ AND $ANC > 1.5 \times 10^9/L$ Or $Platelets > 100 \times 10^9/L \ or$ $50\% \ improvement \ over$ $baseline^b$ Or $Hemoglobin > 11.0 \ g/dL \ or$ $50\% \ improvement \ over$ $baseline \ (untransfused)^b$	Not required	≥ 50% reduction in lymphadenopathy ^c and/or in spleen or liver enlargement
PR with lymphocytosis	Subjects who achieved a PR by IWCLL 2008 criteria in all parameters except lymphocyte count will be considered PR with lymphocytosis. Subjects with a PR with lymphocytosis will not be considered to have achieved a PR until there is a 50% reduction in ALC from baseline was achieved or ALC $<4 \times 10^9$ /L		
SD	Failure to attain CR/PR or progressive disease	Not required	No significant increase or decrease

ANC = absolute neutrophil count; CR = complete remission;

CRi = CR with incomplete blood count recovery; PR = partial remission

- a. Computed tomography (CT) scan of abdomen, pelvis, and chest is required for this evaluation
- b. Without need for exogenous growth factors
- c. In the sum products of ≤ 6 lymph nodes or in the largest diameter of the enlarged lymph node(s) detected before therapy and no increase in any lymph node or new enlarged lymph nodes
- d. Subjects meeting all criteria for a CR with B-lymphocyte nodules on bone marrow exam will be considered nodular partial response (nPR).
- e. The investigator will assess response in subjects with limited tumor burden at baseline using only the parameters that were abnormal at baseline.
- f. If all hematological parameters were normal at baseline (eg, Hbg >11g/dL, Plt >100 x 10^9 /L, ANC >1.5 x 10^9 /L), they must remain normal for the subjects to be considered to have achieved a response.

Progressive disease for CLL is characterized by ≥ 1 of the following:

- Appearance of any new lesion, such as enlarged lymph nodes (> 1.5 cm), de novo appearance of hepatomegaly or splenomegaly, or other organ infiltrates
- An increase of $\geq 50\%$
- in longest diameter of any previous site
- in the previously noted enlargement of the liver or spleen
- in blood lymphocytes with $\geq 5 \times 10^9 / \text{L B}$ cells only in setting of enlarging lymph node, liver, or spleen (note: isolated elevation of WBC by itself will not be considered progressive disease unless subject becomes symptomatic from this)

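### In Appendix 4, footnote f makes CRi unreachable for CLL subjects whose blood counts were all normal at baseline, because it disqualifies the cytopenia that the CRi row requires

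*Protocol*

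**What the plan says.** Appendix 4 sets the blood, marrow and nodal/organ criteria for each CLL response category. Footnote f is attached to the header of the peripheral blood column, not to a single row. Its trigger is "If all hematological parameters were normal at baseline", with hemoglobin above 11 g/dL, platelets above 100 x 10^9/L and ANC above 1.5 x 10^9/L given as examples. Its consequence is that "they must remain normal for the subjects to be considered to have achieved a response". It makes no exception for any row or for drug-related cytopenia.

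Three rows of that column matter here:

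- **CR** requires ANC, platelets and hemoglobin all above the same limits, whatever the baseline.
- **CRi** requires lymphocytes below 4 x 10^9/L together with "Persistent anemia, thrombocytopenia, or neutropenia related to drug toxicity".
- **PR** requires the lymphocyte criterion and any one of ANC, platelets or hemoglobin. PR with lymphocytosis takes over the PR criteria apart from the lymphocyte count.

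Section 6.2.2 includes CRi in its list of objective response categories. Section 6.2 has the investigator assign response. Documented responses are one of the other endpoints in Section 3.3, and Section 8.0 presents them in a listing with no formal test.

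**The concern.** CRi exists to credit a subject who has cleared the disease but whose counts have not recovered because of the drug. Footnote f withholds any response from a subject whose counts were all normal at baseline and then fall. Both apply in the same column of the same table, and nothing says which prevails. In that subset, the finding that qualifies a subject for CRi is the finding that bars a response.

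At stake is the consistency of a stated endpoint. One investigator may follow the row and record CRi, while another follows the footnote and records no response for the same findings. The table offers the second investigator no clean alternative. A subject who meets the CRi row has nodes that have returned to normal, whereas the SD row expects no significant change in nodes, liver or spleen, and the CLL progression criteria are not met.

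**Working it through.** The protocol states no figure on this point, so there is none to reproduce. The check is one of logic: do the rows and the footnote admit the same subjects?

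**Inputs, all from Appendix 4.** There are three counts (ANC, platelets, hemoglobin), each either above its limit or not. That gives 2 x 2 x 2 = 8 baseline patterns and 8 on-treatment patterns.

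**Assumptions.**
- The lymphocyte, nodal and marrow criteria are met.
- Any cytopenia is drug-related.
- A cytopenia in the CRi row means a count below the limit that the CR row and footnote f use. The CRi row gives no thresholds of its own.
- The PR row's alternative of a 50% improvement over baseline is not credited. A count that starts above its limit and falls below it could not meet that alternative anyway.

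**Rules.**
- CRi row: at least one count below its limit. 8 - 1 = 7 patterns qualify.
- PR row: at least one count above its limit. 8 - 1 = 7 patterns qualify.
- Footnote f, if all three were normal at baseline: all three must still be above their limits. 1 pattern qualifies.
- Footnote f, if any count was abnormal at baseline: not triggered, so all 8 patterns pass.

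| Baseline | CRi row | CRi row and footnote f | PR row | PR row and footnote f |
|---|---|---|---|---|
| All three normal (1 of 8 patterns) | 7 | 0 | 7 | 1 |
| At least one abnormal (7 of 8 patterns) | 7 | 7 | 7 | 7 |

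**CRi.** With all counts normal at baseline, the row and the footnote have no pattern in common (7 against 0). CRi cannot be reached as written.

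**PR.** In the same subset, 7 - 1 = 6 patterns are PR by the row and non-response by the footnote. Here the two rules overlap in one pattern, so they can be applied together, and the footnote then acts as a stricter condition.

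**CR.** The row already demands all three counts above the same limits, so footnote f changes nothing.

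These are counts of patterns, not proportions of subjects. The protocol does not say how many CLL subjects had all counts normal at baseline.

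**The case against.** The best defense is that footnote f does useful work. A subject with all counts normal at baseline meets the one-of-three PR requirement before any treatment, so for that subject the row alone tests nothing about ANC, platelets or hemoglobin. Asking that the counts stay normal supplies a test. This stands for PR: the footnote can be a deliberate added condition, and the 6 discordant patterns do not prove an error. The protocol should only say that this is intended. The defense does not reach CRi, where no pattern satisfies both rules.

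One could also say that the list in Section 6.2.2 includes SD and PD, so being on it does not make CRi a response. That is true of the list, but the same section names CRi as a form of complete response.

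Four stronger readings are tempting, and the protocol does not support them:

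- **That any normal count that falls removes the response.** The trigger requires all counts to have been normal. A subject with one abnormal baseline count is untouched, even if a normal count later drops.
- **That footnote f also contradicts footnote e.** Footnote e reads "The investigator will assess response in subjects with limited tumor burden at baseline using only the parameters that were abnormal at baseline". It is limited to low tumor burden and is attached to the nodes, liver and spleen column. The two meet only if footnote e is read across all columns, in subjects who have both limited burden and all-normal counts.
- **That the share of subjects affected can be estimated.** Section 1.4.1 gives 16.4% Grade 3 or 4 neutropenia on study drug in the randomized CLL/SLL study. That is the incidence of reported events, not the prevalence at a response assessment. Using it would need an assumed all-normal share, independence of neutropenia from baseline counts, and the chance that the subject otherwise qualifies as a responder.
- **That a response rate is biased.** Section 8.0 plans a listing of responses and no test.

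**Conclusion.** The conflict between footnote f and the CRi row is real and should be corrected. For CLL subjects with hemoglobin, platelets and ANC all normal at baseline, CRi is unreachable as written, and a subject who meets the CRi row is a non-responder under the footnote. This rests on the footnote's place on the column header, on the absence of any exemption, and on reading cytopenia as a count below the stated limits.

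The practical size is modest. Only the all-normal subset is affected, and the protocol does not give its size. Only the descriptive listing of responses is affected. The CLL progression criteria contain no cytopenia criterion, and lack of response is not among the reasons for stopping treatment in Section 4.3, so neither the PD endpoint nor continued treatment is touched. Under Section 6.2.1 the baseline tumor assessment generally comes from the parent study, so some responses may have been established before entry, which narrows the effect further.

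On PR and PR with lymphocytosis the protocol is unclear rather than contradictory.

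**What to change.** Amend footnote f in two respects:

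1. State that it does not apply to the CRi row.
2. State whether it is meant as an added condition on PR and PR with lymphocytosis, whose row asks for only one of the three counts.

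Two broader changes are better avoided. Limiting footnote f to CR would empty it, because the CR row already sets the same limits for everyone. A general exemption for drug-related cytopenia in every category would need relatedness judgments that the study does not collect for most low-grade events, since Section 7.1.1 restricts AE recording largely to Grade 3 or 4 plus listed exceptions.

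The cost is a change of wording in one footnote. Hematology is already collected. Responses in CLL subjects with all-normal baseline counts that were recorded under the present text should be checked against the amended footnote. The downside is that CRi in this subset will rest on the investigator's attribution of the cytopenia to the drug in an open-label study, but the CRi row already requires that judgment.

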Appendix 5. Response Assessment Criteria for Lymphoma (Cheson 2007)¹⁰

Response	Definition	Nodal Masses	Spleen, Liver	Bone Marrow
CR	Disappearance of all evidence of disease	(a) FDG-avid or PET positive prior to therapy; mass of any size permitted if PET negative (b) Variably FDG-avid or PET negative; regression to normal size on CT	Not palpable, nodules disappeared	If infiltrate present at screening, infiltrate cleared on repeat biopsy; if indeterminate by morphology, immuno- histochemistry should be negative
PR	Regression of measurable disease and no new sites	≥ 50% decrease in SPD of up to 6 largest dominant masses; no increase in size of other nodes (a) FDG-avid or PET positive prior to therapy; ≥1 PET positive at previously involved site (b) Variably FDG-avid or PET negative; regression on CT	≥ 50% decrease in SPD of nodules (for single nodule in greatest transverse diameter); no increase in size of liver or spleen	Irrelevant if positive prior to therapy; cell type should be specified
SD	Failure to attain CR/PR or progressive disease	(a) FDG-avid or PET positive prior to therapy; PET positive at prior sites of disease, and no new sites on CT or PET (b) Variably FDG avid or PET negative; no change in size of previous lesions on CT		

Abbreviations: CR = complete response, CT = computed tomography, FDG = [¹⁸F]fluorodeoxyglucose, PET = positron-emission tomography, PR = partial remission, SD = stable disease, SPD = sum of the product of the diameters

Progressive disease for Non-Hodgkin's lymphoma is characterized by any new lesion or increase by $\geq 50\%$ of previously involved sites from nadir for example:

- Appearance of a new lesion(s) > 1.5 cm in any axis, $\ge 50\%$ increase in SPD of > 1 node, or $\ge 50\%$ increase in longest diameter of a previously identified node >1 cm in short axis
- Lesions PET positive if FDG-avid lymphoma or PET positive before therapy
- > 50% increase from nadir in the SPD of any previous lesions in the liver or spleen
- New or recurrent involvement in the bone marrow

An increase of \geq 50% in blood lymphocytes with \geq 5 x 10⁹/L B cells only in setting of enlarging lymph node, liver, or spleen (note: isolated elevation of WBC by itself will not be considered progressive disease unless subject becomes symptomatic from this)

Appendix 6. Response Assessment Criteria for Waldenström's Macroglobulinemia (Kimby 2006)¹¹

Response	Definition
CR	A disappearance of serum and urine monoclonal protein determined by immunofixation, absence of malignant cells in bone marrow determined by histologic evaluation, resolution of adenopathy/organomegaly, (confirmed by computed tomography [CT] scan), and no signs or symptoms attributable to WM. Recommendation of the CR status is required ≥ 6 weeks later with a second immunofixation.
PR	$A \ge 50\%$ reduction of serum monoclonal IgM concentration determined by protein electrophoresis, $\ge 50\%$ decrease in adenopathy/organomegaly on physical examination or on CT scan, and no new symptoms or signs of other active disease.
SD	A < 25% reduction and < 25% increase of serum monoclonal IgM determined by electrophoresis without progression of adenopathy/organomegaly, cytopenias, or clinically significant symptoms caused by disease and/or signs of WM.
PD	$A \ge 25\%$ increase in serum monoclonal IgM by protein electrophoresis confirmed by a second measurement or progression of clinical significant findings caused by disease (eg, anemia, thrombocytopenia, leukopenia, or bulky adenopathy/organomegaly) or symptoms (eg, unexplained recurrent fever $\ge 38.4^{\circ}$ C, drenching night sweats, $\ge 10\%$ weight loss, hyperviscosity, neuropathy, or symptomatic cryoglobulinemia) attributable to WM.

Abbreviations: WM=Waldenström's Macroglobulinemia, CR = complete response, CT = computed tomography, PR = partial response, SD = stable disease, PD=progressive disease

Appendix 7. Child-Pugh Score^{22,23}

Measure	1 point	2 points	3 points
Total bilirubin, μmol/L (mg/dL)	<34 (<2)	34-50 (2-3)	>50 (>3)
Serum albumin, g/L (g/dL)	>35 (>3.5)	28-35 (2.8-3.5)	<28 (<2.8)
PT INR	<1.7	1.71-2.30	>2.30
Ascites	None	Mild	Moderate to Severe
Hepatic encephalopathy	None	Grade I-II (or suppressed with medication)	Grade III-IV (or refractory)

Points	Class
5-6	A
7-9	В
10-15	С
